# **FULL PROTOCOL TITLE: The Impact of Contact Lens Coefficient of Friction (CoF) on the Development of Lid Wiper Epitheliopathy (LWE)**

## **1.0 Objectives**

The primary study objectives are to determine the amount of Lid Wiper Epitheliopathy (LWE) induced in subjects after contact lens fitting that do not have LWE at study enrollment. Subjects in the trial will be fit in 2 contact lenses with different coefficients of friction (CoF). One eye will be fit in a contact lens with a low coefficient of friction (Acuvue Oasys®, Johnson & Johnson Vision, Jacksonville FL) while the contralateral eye will be fit in a contact lens with a high CoF (Air Optix® Night & Day® Aqua, Ft. Worth, TX), as reported in the scientific literature. The eye receiving each lens will be assigned randomly. The presence of LWE will be assessed at 2 different time points:

- Approximately 2 hours after contact lens fitting and
- After 7( $\pm 2$ ) days of contact lens wear

**Study Hypotheses:** Contact lenses with a greater coefficient of friction will induce a greater amount of LWE than contact lenses with a lower coefficient of friction. The presence of LWE will be assessed at 2 different study time points. As such, the following hypotheses will be tested:

After one week of contact lens wear

- $H_{01}$ : There is no statistically significant difference in the amount of LWE between contact lenses with different coefficients of friction
- $H_{a1}$ : There is a statistically significant difference in the amount of LWE between contact lenses with different coefficients of friction

After 2 hours of contact lens wear

- $H_{02}$ : There is no statistically significant difference in the amount of LWE between contact lenses with different coefficients of friction
- $H_{a2}$ : There is a statistically significant difference in the amount of LWE between contact lenses with different coefficients of friction

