### **5.0 Number of Subjects**

The proposed single-site study will be conducted at The Ocular Surface Institute at the University of Houston College of Optometry. Up to 60 subjects will be screened for study inclusion, with the goal of completing 20 subjects. Subjects that screen fail may be rescreened for study inclusion up to 3 additional times at the discretion of the study investigator.

Currently, there is no information on the time from contact lens fitting to the development of LWE. This pilot study is designed to collect data which can be used to determine the sample size required to conduct a larger-scale clinical trial. It is anticipated that enrolling 20 subjects will approach the requirements of the central limit theorem for statistical analysis. Since the subjects in the study will be wearing FDA-approved contact lenses on a daily wear modality (i.e. not sleeping in contact lenses), the study does not present more than minimal risk to the subject and a power analysis is not required.

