## **7.0 Study Endpoints**

The primary study endpoints are as follows:

- Examine the development of LWE post-contact lens fitting at the following time points
  - 1-week post contact lens fitting
  - 2 hours after contact lens fitting

The secondary study endpoints are as follows:

- Examine the level of expression in ocular surface tear MMPs post-contact lens fitting at the following time points
  - Pre-contact lens fitting
  - 1-week post contact lens fitting
  - 2 hours after contact lens fit

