## **FULL PROTOCOL TITLE: The Impact of Contact Lens Coefficient of Friction (CoF) on the Development of Lid Wiper Epitheliopathy (LWE)**

### Addendum: Statistical Analyses

Statistical analyses were performed in SPSS v26 (IBM) and GraphPad. When data were not significantly different from a normal distribution (non-invasive tear break up time, tear meniscus height), statistical analyses were conducted using paired t-tests and repeated-measures analyses of variance (RM-ANOVA), with adjusted post-hoc t-tests, when appropriate. For NITBUT and TMH, the RM-ANOVA included two repeated factors—lens type (Acuvue Oasys and Air Optix Night and Day) and time (baseline, 2 hours post-fitting and 7 days after lens fitting). For data that was not normally distributed (LWE staining), Friedman and Mann-Whitney non-parametric statistics were performed. MMP concentrations were adjusted by multiplying raw values by the dilution factor. Tear film MMP concentrations under the level of detection (LOD) were divided by  $\sqrt{2}$  (Croghan et al. 2003). Outliers in MMP data sets were analyzed using the ROUT function in Graphpad Prism 8.4.1 and were removed prior to analysis.

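### The primary objective and endpoint claim LWE caused by lens fitting, but only the randomised between-lens difference can be attributed; a change from baseline can arise with no lens effect

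*Combined protocol and SAP*

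**What the plan says.** **Aim.** Section 1.0 opens with the objective to "determine the amount of Lid Wiper Epitheliopathy (LWE) induced in subjects after contact lens fitting that do not have LWE at study enrollment". The primary endpoint in Section 7.0 is to "Examine the development of LWE post-contact lens fitting at the following time points", namely 1 week and 2 hours.

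**Design.** Section 1.0: "One eye will be fit in a contact lens with a low coefficient of friction", the "contralateral eye will be fit in a contact lens with a high CoF", and "The eye receiving each lens will be assigned randomly". No eye goes unworn, and there is no group without lenses.

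**Hypotheses.** H01 (1 week) and H02 (2 hours) share one null: "There is no statistically significant difference in the amount of LWE between contact lenses with different coefficients of friction". No hypothesis concerns change from baseline.

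**Selection.** Section 3.0 excludes upper-lid LWE above 0.5 in height or width, assessed at the pre-fit visit. Section 5.0 adds: "Subjects that screen fail may be rescreened for study inclusion up to 3 additional times at the discretion of the study investigator". Up to 60 are screened to complete 20. Step 1.1.12 in Section 8.0 states the reverse rule: subjects with no LWE in both eyes are discontinued, and those with LWE in either eye continue.

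**Analysis.** The addendum says: "For data that was not normally distributed (LWE staining), Friedman and Mann-Whitney non-parametric statistics were performed". It does not say which factor each test covers. Time (baseline, 2 hours, 7 days) is named as a factor only for tear break-up time and tear meniscus height.

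**The concern.** An induced amount of LWE is a causal quantity: LWE after wear, minus what the same lids would have shown without a lens. The second term is never observed here. The only lens-free LWE assessment is the pre-fit one, and that is also the visit at which subjects are selected on LWE.

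Two things other than lens wear can then move the score:

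- **Regression to the mean.** People admitted because a noisy reading was low will on average read higher next time. Repeat attempts after a failure strengthen this, since a subject whose usual grade is too high can enter on one favourable reading.
- **Repeated procedures.** Two drops of dye are instilled at step 1.1.12 and two more at step 1.2.5, about 2 hours after lens insertion, with lid handling each time and no untreated comparison.

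At stake is a report that lenses cause LWE within 2 hours or a week of fitting when some or all of the rise is an artefact. Section 2.0 says the speed of onset is currently unknown, so this is a result readers would look for.

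**Working it through.** **No plan figure to reproduce.** The target of 20 rests on an appeal to the central limit theorem, with no effect size, SD or power, so it cannot be rebuilt. The documents do fix one bound: 20 completers from at most 60 screened gives a lowest overall pass fraction of 20/60 = 1/3.

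**Inputs from the documents.** 20 subjects; a height and a width grade per eye, averaged to the final score; entry if no grade exceeds 0.5; 0 or 3 rescreens; three gradings (baseline, 2 hours, 7 days); significance at p ≤ 0.05.

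**Assumed inputs.** The share of grade variance that is stable over time (ICC) is 0.6 to 0.9 in the main table. The fraction passing a single LWE screening is 1/3, 0.5 or 0.8. Between-eye correlation is 0.7. Grades move in steps of 0.5, spaced 0.4 SD apart. Both eyes must pass. In the rescreen setting every failure is rescreened. Errors at the three gradings are independent.

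**Step 1: expected drift by hand.** With no lens effect, the expected rise is approximately

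(1 − ICC) × (population mean − mean of those selected).

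With one screening:

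| ICC | Pass fraction | Population mean | Selected baseline | Rise by formula | Simulated rise |
|---|---|---|---|---|---|
| 0.9 | 1/3 | 0.71 | 0.08 | 0.1 × 0.63 = 0.06 | 0.15 − 0.08 = 0.07 |
| 0.8 | 1/3 | 0.71 | 0.08 | 0.2 × 0.63 = 0.13 | 0.22 − 0.08 = 0.14 |
| 0.6 | 1/3 | 0.70 | 0.08 | 0.4 × 0.62 = 0.25 | 0.34 − 0.08 = 0.26 |
| 0.6 | 0.5 | 0.45 | 0.06 | 0.4 × 0.39 = 0.16 | 0.23 − 0.06 = 0.17 |

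Formula and simulation agree to about 0.01 grade.

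**Step 2: how often Friedman over time rejects with no lens effect** (one eye, three times, 600 trials per setting):

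| ICC | Pass fraction | One screening | Up to 3 rescreens |
|---|---|---|---|
| 0.9 | 1/3 | 19% | 35% |
| 0.9 | 0.5 | 11% | 26% |
| 0.8 | 1/3 | 28% | 52% |
| 0.8 | 0.5 | 17% | 34% |
| 0.6 | 1/3 | 53% | 73% |
| 0.6 | 0.5 | 31% | 50% |
| 0.6 to 0.9 | 0.8 | 4% to 10% | 8% to 14% |

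Simulation error is about 2 points (for 53%: √(0.53 × 0.47/600) = 0.020). At ICC 0.95, over all three pass fractions, the rates are 3% to 11% with one screening and 5% to 23% with rescreens. At ICC 1.0 the rate is 0%.

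**Step 3: is selection the cause?** With no selection on the analysed baseline, the same test rejects in 3.8% to 4.9% of trials.

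**Step 4: the randomised contrast.** Under the same selection, the between-lens test at 7 days rejects in 1.3% to 6.5% of trials with the Wilcoxon signed-rank test and 0.3% to 3.8% with Mann-Whitney. The latter is conservative because it ignores the pairing of eyes.

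**Step 5: the reverse rule in step 1.1.12.** If only subjects with LWE continue, the drift is downward (for example 1.03 to 0.96 at ICC 0.8, pass fraction 1/3), and rejection is 7% to 21%.

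**Step 6: a different grading model.** With a final score in steps of 0.25, mean 0.5, SD 0.6, between-eye correlation 0.6 and ICC 0.7, and both eyes at 0.5 or below, reruns gave about 14% to 19% with one screening and 27% to 36% with up to four. The mechanism survives a change of model; the exact rate does not.

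**The case against.** **The hypotheses already ask the right question.** H01 and H02 are randomised within-subject contrasts, and the protocol title and Section 2.0 frame the study as high against low friction. This stands. A reader might infer that the trial's main comparison is biased; it is not, because both eyes are selected and handled alike.

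**Friedman over time is not a stated plan.** This also stands. With two lenses and three gradings, time is the likely Friedman factor, but the addendum does not say so. Nor do the documents say that a rise would be reported as caused by lenses, or that it would size the larger trial. Section 5.0 does not name the quantity to be used for that.

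**The analysed baseline may not be the eligibility grade.** Photographs are taken at step 1.1.13, after the eligibility examination, and Section 8.0 has photographs de-identified and graded. An independent photo grade would not carry over the grading error from screening, so less drift would be expected. Same-day variation in staining would remain. Visit 1.2 lists no photography step, so the source of the 2-hour grade is unclear. This stands in part.

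**Two hours is the same day.** Day-to-day variation cannot explain a rise between Visits 1.1 and 1.2, yet the simulation draws fresh error at 2 hours. This is fair: the simulated 2-hour drift is an upper reading, and what remains at that time is grading error and the repeated dye and handling.

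**Rescreening is discretionary.** The rescreen figures assume that every failure returns, so they mark the upper end.

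None of this supplies the missing lens-free comparison.

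**Conclusion.** The point holds as a limit on attribution. The objective and endpoint promise LWE caused by fitting, while the design supports only a difference between two lenses. A change from baseline can arise from selection, dye or handling alone.

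It does not follow that the plan will show LWE developing when there is no effect. The false-positive rate of a Friedman test over time, if one is run, spans 0% with perfectly stable grades, 4% to 10% when 80% pass a single screening, and 11% to 73% for ICC 0.6 to 0.9 and pass fraction 1/3 to 0.5, with or without rescreens. Grading repeatability and pass fraction decide where the trial falls, and the documents give neither. The direction is also open: upward under Sections 1.0 and 3.0, downward under step 1.1.12 as written.

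H01 and H02 are unaffected. For a pilot whose formal hypotheses are sound, this is an inexpensive correction to the stated aim and to how change over time is interpreted.

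**What to change.** 1. In Sections 1.0 and 7.0, word the primary objective and endpoint as the between-lens difference in LWE at 1 week and at 2 hours, matching H01 and H02.
2. Report change from baseline within each lens as descriptive. State that, with no unworn eye or lens-free follow-up and with selection at the baseline visit, it cannot be attributed to lens wear.
3. In the addendum, state which factor the Friedman test covers and whether the analysed LWE grade comes from the slit lamp or the photographs. Do not use a Friedman test over time as evidence that lenses induce LWE.
4. Report the number of screenings for each enrolled subject.
5. Reconcile step 1.1.12 with Sections 1.0 and 3.0 on which subjects continue, since the direction of the selection effect depends on it.

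The addendum is written in the past tense; if the analysis is already done, items 2 to 4 belong in the report.

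The cost is wording and one extra tabulation, with no new data. What is given up is a causal claim about LWE onset after fitting, which this design cannot support.

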## **FULL PROTOCOL TITLE: The Impact of Contact Lens Coefficient of Friction (CoF) on the Development of Lid Wiper Epitheliopathy (LWE)**

While CoF is a useful laboratory metric, it cannot be measured clinically. Therefore, a clinical corollary for CoF may be useful in determining which contact lens materials will minimize the potential for contact lens dropout. A possible clinical corollary for CoF is Lid Wiper Epitheliopathy (LWE), which has been reported to be related to contact lens discomfort. LWE leads to a loss of superficial epithelial cells in the lid wiper region of the eyelid. If CoF is indeed related to contact lens discomfort, subjects wearing a high CoF lens could potentially develop greater amounts of LWE compared to that observed with a low CoF lens.

While previous studies have determined the amount of LWE present in habitual contact lens wearers and non-contact lens patients, it is currently unknown how quickly LWE may develop in patients after contact lens fitting. Development of LWE in the post-contact lens fitting period may allow clinicians to predict the potential for contact lens discomfort and future dropout. This pilot study will collect data examining the development of LWE in the period immediately following contact lens fitting (2 hours post-fit) and after approximately 1 week of contact lens wear, corresponding to the time for a typical post-contact lens fitting assessment in clinical practice.

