## FULL PROTOCOL TITLE: The Impact of Contact Lens Coefficient of Friction (CoF) on the Development of Lid Wiper Epitheliopathy (LWE)

Korb LWE Grading				
Grading	Description	Height (%)	Width (mm)	Final score (grade)
0	no LWE	<25	<2	<0.25
1	mild LWE	25-50	2-4	0.25-1.00
2	moderate LWE	50-75	5-9	1.25-2.00
3	severe LWE	>75	>10	2.25-3.00

\*Final LWE score is the average of the LWE Height and Width

The tears collected by capillary tubes will be stored at -80°C until luminex multibead analysis. 15 µg of total protein will be analyzed for matrix metalloproteinases (MMP)-1, -2, -7, -9, -10. Pre- and post-contact lens wear concentrations of MMP will be compared for each subject. MMPs are a family of zinc proteases and an increase in MMP expression occurs in response to a wide range of stimuli, including adhesion molecules, growth factors, cytokines and hormones and is associated with ocular surface damage. The correlation coefficient, r, will be determined between LWE and the tear film levels of MMPs.

A  $p \leq 0.05$  will be considered statistically significant.

Layman's Description of Procedures	
Patient demographics	The subjects will be asked questions about their age, sex, race and ethnicity.
History	The subjects will be asked questions about their systemic health, ocular disease and surgical history.
Concomitant Medications	The subjects will be asked questions about their current ocular and systemic medications.
Habitual Contact Lens Information	The subjects will be asked questions about how they use their current contact lenses, such as their current contact lens brand and wear time, as performed during a normal eye exam.
Auto-refraction	A machine will shine light into a subject's eye and will estimate their prescription using different powered lenses without making contact with the eye.
Oculus Keratograph	A machine uses a video camera to determine how long it takes for a subject's tear film to

**FULL PROTOCOL TITLE: The Impact of Contact Lens Coefficient of Friction (CoF) on the Development of Lid Wiper Epitheliopathy (LWE)**

	evaporate and the height of the pooled tears between the lower lid and the ocular surface without making contact with the eye.

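### The lenses are compared on fellow eyes, but the addendum names an unpaired test for LWE, and no rule says whether one or both primary time points must be positive for an overall claim

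*Combined protocol and SAP*

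**What the plan says.** Section 1.0 (Objectives) describes a contralateral design. One eye gets the low-friction lens and "the contralateral eye will be fit in a contact lens with a high CoF", with the eye assigned at random. The study hypothesis is a single directional statement: "Contact lenses with a greater coefficient of friction will induce a greater amount of LWE than contact lenses with a lower coefficient of friction". The text continues: "The presence of LWE will be assessed at 2 different study time points. As such, the following hypotheses will be tested". Two pairs of hypotheses follow, H01/Ha1 after one week and H02/Ha2 after 2 hours. Both alternatives are non-directional.

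Section 7.0 (Study Endpoints) puts both times under the primary endpoint, "Examine the development of LWE post-contact lens fitting at the following time points", with "1-week post contact lens fitting" listed first. Tear MMPs are secondary. Section 8.0 gives the only threshold in the documents: p at or below 0.05 "will be considered statistically significant".

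The addendum (Statistical Analyses), written in the past tense, assigns paired t-tests and RM-ANOVA to tear break-up time and tear meniscus height. Adjusted post-hoc tests are mentioned only there. For LWE it names Friedman and Mann-Whitney, without saying which comparison each served. It gives no order, alpha split or adjustment for LWE. No section says whether support for the hypothesis needs one time point or both.

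**The concern.** There are two linked gaps. First, the lens comparison is within subject, and Mann-Whitney assumes independent groups. Fellow eyes usually resemble each other, so the unpaired test overstates the variance of the difference. It then rejects too rarely under the null and misses real differences.

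Second, the excess conservatism hides a multiplicity question. Two primary tests serve one headline statement. With the pairing corrected, each test has its intended 5% size. Whether the overall claim then carries more than one test's error depends on a success rule that is not written down. Together the gaps leave the reader unsure what error rate attaches to a statement that higher friction induces more LWE.

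**Working it through.** There is no planned figure to reproduce. The protocol gives a threshold (0.05) and a target of 20 completers, but no power, effect size, SD or familywise error rate.

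**Inputs.** From the documents: two primary nulls, 0.05 per test (read as two-sided), 20 pairs of eyes. Assumed, because the documents do not give them: between-eye correlation, between-time correlation and the LWE score distribution.

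**Step 1: size of Mann-Whitney on paired eyes.** If the ranks of fellow eyes have correlation r, the true variance of the rank difference is about (1 − r) times what the test assumes. In large samples:

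size ≈ 2[1 − Φ(1.96/√(1 − r))]

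- r = 0.3: 1.96/0.837 = 2.34, size about 1.9%
- r = 0.5: 1.96/0.707 = 2.77, size about 0.6%
- r = 0.7: 1.96/0.548 = 3.58, size below 0.1%

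Simulation with 20 pairs, cutting a latent normal variable into an assumed skewed score, gave about 2.4%, 1.0% and 0.2% at latent correlation 0.3, 0.5 and 0.7. These are slightly higher because cutting into grades lowers the rank correlation. The direction and order of magnitude agree.

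**Step 2: either-time error with the unpaired test.** If the two times are independent, 1 − (1 − 0.024)² = 4.7%, 1 − (1 − 0.010)² = 2.0% and 1 − (1 − 0.002)² = 0.4%. Simulation with correlated times gave about 4.0–4.6%, 1.8–2.1% and 0.4%. Only with uncorrelated eyes did it reach 8.2–9.6%.

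**Step 3: either-time error with a correctly sized paired test.** For independent tests, 1 − 0.95² = 9.75% for any rejection, and 1 − 0.975² = 4.94% for rejection in the stated direction. For correlated statistics (bivariate normal, both nulls true):

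| Between-time correlation | Any rejection | Stated direction | Holm, any | Holm, stated direction |
|---|---|---|---|---|
| 0 | 9.75% | 4.9% | 4.9% | 2.5% |
| 0.5 | 9.1% | 4.5% | 4.65% | 2.3% |
| 0.8 | 7.8% | 3.9% | 4.0% | 2.0% |
| 0.9 | 7.0% | 3.5% | 3.6% | 1.8% |

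One test alone gives 5% and 2.5%. If both time points are required, the null probability of two rejections runs from 0.25% (independent) to 5% (correlation 1), so nothing is inflated. In the simulated scores, signed-rank tests gave 7.9–9.2% for any rejection, 4.1–4.6% in the stated direction and 3.4–4.2% for any rejection under Holm.

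**Step 4: power.** In simulation on assumed scores, signed-rank with Holm was compared with unadjusted Mann-Whitney:

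- between-eye correlation 0.5, one time differs: 77% against 69%
- between-eye correlation 0.3, one time differs: 61% against 66%
- between-eye correlation 0.3, both times differ: 70% against 67%

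Against an unadjusted signed-rank test set to 80% power, Holm gives about 67–69% if one time differs and 73–77% per hypothesis if both do.

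**The case against.** The strongest case is that no multiplicity problem exists. Each null has its own time heading, and section 2.0 gives the times different purposes; not knowing "how quickly LWE may develop in patients after contact lens fitting" makes 2 hours and one week separate questions. Reported that way, each test keeps its own 5% error. This stands, and it is why the inflation is conditional. What remains is that one directional hypothesis introduces both nulls, and nothing prevents an overall claim from either.

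One week is numbered first and listed first among the endpoints, although the assessment bullets in section 1.0 run chronologically. That may hint at a lead time point, but no text calls it a testing order.

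Friedman is a within-subject test and could have served as an omnibus gate, or even for the lens comparison. The addendum does not say so, hence the condition that Mann-Whitney was run on fellow eyes as independent groups.

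The study is a pilot meant to size a larger trial, both tests were stated in advance, and a reader shown both p-values can weigh them. That limits the importance of the multiplicity part. It does not excuse an unpaired test on paired data.

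A reader might go further and infer that the plan allows a lone p-value to count as the positive primary result. It does not: section 8.0 gives a per-test threshold, and silence on success is not an either-suffices rule. Nor do the documents support an error near 10% for the analysis as named. In simulation, unpaired Mann-Whitney kept either-time error below 5% at between-eye correlation of 0.3 and above. That is a by-product of the wrong test, not a control.

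**Conclusion.** The point holds as a minor one, in two parts. The firmer part is pairing: if the Mann-Whitney test compared fellow eyes as independent groups, its per-test size is about 2.4% to 0.2% at between-eye correlation 0.3 to 0.7, and power is lost. The exact values rest on an assumed score distribution and assumed correlations.

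The second part is conditional. With a correctly sized paired test, and only if one headline claim may rest on either time point, the chance of a false rejection is 7.0–9.75% for between-time correlation 0.9 down to 0. In the direction that the hypothesis states, it is 3.5–4.9% against 2.5% for one test, and never above 5%. The documents adopt none of the possible rules (either, both, or separate reporting), so the inflation is a possibility to close off, not an established property of the plan. The MMP analyses are outside this point; section 7.0 already ranks them as secondary.

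**What to change.** In the addendum, compare the lenses at each time point with a paired test, such as the Wilcoxon signed-rank. Report both within-subject differences with confidence intervals and unadjusted p-values, as time-specific results. State which comparisons the Friedman test covered.

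If one overall claim that higher friction induces more LWE is drawn from either time point, base it on Holm-adjusted p-values across H01 and H02: the smaller p against 0.025 and, only if that is met, the larger against 0.05. Disclose that this was added afterwards.

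The cost is a short addendum paragraph and a re-analysis of existing data. Holm loses some power relative to an unadjusted paired test. From a between-eye correlation of about 0.3 upward, the gain from pairing offsets that loss largely or wholly, on the illustrative figures above. The unadjusted results stay visible, so nothing needed to size the larger trial is lost.
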